### **Data analysis;**

The number of household contacts **expected** will be calculated as the number of index cases times the average number of household contacts identified in the same countries, or countries with similar resource levels (based on World Bank classification of national income level), from two recent systematic reviews (Fox and Morrison). This will be compared to the number actually identified.

We will match the problems identified with each step in the Cascade associated with more than 10% losses/drop-outs, based on the Indicator review. For example if a large number of identified contacts are not initially screened (in the systematic review, we found that 30% of identified contacts were lost at this stage), then we will identify problems associated with that step in the Cascade and prioritize identifying interventions to address these (See Figure 3 for schematic). The problems to be addressed may have been identified from questionnaires completed by patients with active TB, their contacts, or the health care

providers. Simple proportions will be estimated at each centre, corrected for clustering at the household level via generalized estimating equations.

### **Reporting findings:**

The final step of Phase 1, and really the transition to Phase 2, is the presentation of the findings to TB control authorities in each jurisdiction (ie at municipal, state or provincial levels), and to local health authorities, who will be involved in the selection, and implementation of corrective interventions.

### **TIMETABLE FOR PHASE 1:**

Months 0-3: Cascade indicators & Interviewer administered questionnaires at each clinic/facility.

Months 4-5: Data analysis, preparation of reports, identification of potential solutions with options analysis.

Months 5-6: Presentations/discussions with TB control officials at national/state/municipal levels and responsible officials at Health facilities.

### **ETHICAL CONSIDERATIONS – PHASE 1**

This protocol will be submitted for review by ethics review committees at the coordinating centre, and the coordinating centres in each country.

Informed consent will be obtained for all workers, index cases, and contacts before they complete questionnaires or participate in interviews. For the Cascade indicators, only non-nominal data will be abstracted, so consent from patients included in the registries or other information sources will not be sought. However approval from the responsible health officials at participating facilities will be obtained.

Mechanisms to protect confidentiality are the following. Only non-nominal data will be extracted from index case registries, and treatment cards, and from other sources of information for Cascade indicators. Nominal information of participants in questionnaires and interviews will be kept in separate files, under lock and key in the offices of the coordinating centres in each country. This information will not be entered into electronic files - only a unique study ID assigned to each participant. In public presentations no individual identities will be revealed.

### **DETAILS OF METHODS OF PHASE 2 OF THE STUDY:**

#### **STUDY POPULATION:**

The participants are the household contacts of newly diagnosed patients with microbiologically confirmed active PTB. The intervention and control sites are also the same as in Phase 1.

#### **Sample size considerations:**

As seen in Table 1 above (Study population), we estimate that during the 18 months of the study, 2475 active TB cases will be diagnosed at the participating sites, and 10,425 contacts will be identified, of whom 4975 will be diagnosed with LTBI. We wish to detect a 15% increase in the proportion of contacts that initiate therapy, with a level of statistical significance of 0.05 (alpha error). The intra-class correlation coefficient (ICC) which describes the inter-cluster heterogeneity, (or analogously the correlation amongst subjects in the same cluster) has less effect, but to be conservative we will assume this to be 0.05 to 0.1– which is high. In data from the 9INH vs 4RIF trial (comprising 6031 adults treated for latent TB in 12 centres), the ICC for the centre effect was low – just 0.01-0.02, depending on the method used to estimate it, for treatment completion. We will have 24 clusters in 5 countries. Our power calculations are based on the number of close contacts identified per randomization unit (from Table 1).

**Table 2: Detectable differences with all sites in all countries** (alpha=.05, and Power = 80%)

Proportion starting LTBI therapy in Control Arms	N Contacts per clinic	Design Effect	Total sample size per arm	Intra-Class Correlation	Detectable difference
0.10	100	2.0	1222	0.01	0.05
0.10	100	6.0	1214	0.05	0.10
0.10	100	10.9	1199	0.10	0.14
0.30	100	2.0	1236	0.01	0.08
0.30	100	6.0	1261	0.05	0.13
0.30	100	10.9	1221	0.10	0.18

Therefore, given 24 clusters in 5 countries, with at least 100 contacts per site every 6 months (based on minimum 40 active cases every year, and estimated 4.2 contacts per index case), and assuming that at baseline only 10% of contacts are started on Latent TB therapy, plus an ICC of 5%, we would have 80% power to detect a 10% increase in proportion of contacts starting therapy. If the number of contacts per site is higher this will actually have a modest effect on the detectable difference. If the proportion starting therapy is much higher (30%), then the detectable difference would be near 13%.

The resources and prior staff experience in LTBI care at the Canadian sites are very different from that of the sites in the LMIC. This makes it likely there will be better pre-intervention outcomes in Canada, potentially limiting the need for, and impact of certain interventions. The other 5 countries are also different – with regard to resources, availability of trained health workers, and patient populations. This may result in large differences in the baseline situation, and intervention effect size. Hence secondary analysis is planned to estimate the intervention effect within each country. Since Canada has the smallest numbers we estimated the power to detect differences in Canada alone, as shown in Table 3.

**Table 3: Detectable differences in Canada alone** (alpha=.05, and Power = 80% )

Proportion starting LTBI therapy in Control Arms	N Contacts per clinic	Design Effect	Total sample size per arm	Intra-Class Correlation	Detectable difference
0.30	50	1.5	150	0.01	0.19
0.30	50	3.5	150	0.05	0.29
0.30	50	5.9	150	0.10	0.37
0.30	100	2.0	300	0.01	0.16
0.30	100	6.0	300	0.05	0.27
0.30	100	10.9	300	0.10	0.36

Therefore in Canada, we should have sufficient power to detect a 27% increase in proportion of infected contacts starting LTBI therapy, if 30% now start therapy. Increasing the number of contacts per cluster (clinic) to 300 would only decrease the detectable difference to 25%.

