### **Study design:**

We propose a cluster randomized trial at 36 sites in 6 countries. Sites randomized to the intervention group will receive a complex two-phase intervention lasting 18 months. Control sites will receive a stream-lined version of this 2-phase intervention after 18 months, while outcomes are continued to be measured at all sites for an added 12 months.

**Randomization** will be stratified by country, and restricted to ensure equal number of participants receiving or not receiving the intervention within each country. Following randomization, **in Phase 1**, a standardized public health evaluation will be conducted at all intervention sites to identify barriers to LTBI diagnosis and treatment initiation, in order to select the solutions to be used in Phase 2. This will include measurement of the key study outcomes (see below). To ensure standardization of data gathering we will use (i) current indicators of the LTBI cascade of care in the participating units (number of contacts per index case registered, investigated, started on treatment and completing treatment) and (ii) interviewer-administered standardized questionnaires – for patients with newly diagnosed active pulmonary TB, household contacts of these patients, clinic staff and administrators. These questionnaires will assess management of contacts, LTBI diagnosis and therapy, as well as TB-related knowledge, attitudes and beliefs from the perspective of these different participants. Results from this phase will be analysed, and used by the investigators, together with local public health officials, to decide on appropriate corrective solutions. In control sites we will gather data on study outcomes only (see below).

**In Phase 2**, solutions will be selected, and implemented at the intervention sites. Preparations and training of staff at each site will be conducted before the intervention begins, as soon as each site (clinic) is judged ready to begin. Study outcomes will continue to be measured at all sites through-out Phase 2.

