# Estimated based on 4.2 contacts identified per active TB case - from systematic review 

## Estimated based on prevalence of LTBI among contacts screened: of 51.5% in LMIC , and 28.1% in Canada .

We anticipate that our study objectives can be met with this number of sites or clinics (which will be the units of randomization) in each country. This number of sites is considered optimal for several reasons: i) ensures variation in clinic staff, setting and population; ii) avoids experience overly skewed by one or two high performing (or poorly performing) clinics;

Each site should have an adequate number of contacts – but this may be unknown before Phase 1 begins. Hence each unit of randomization (ie each clinic), should have diagnosed an annual average of at least 40 patients with active pulmonary TB in each of the preceding 3 years - in order to have enough contacts to study (from prior systematic reviews, on average 4.2 household contacts are identified per active PTB patient in LMIC).

A narrative description of the functioning of the TB programme, particularly contact investigation, at each site will be written by the research staff, with the input of a member of the site's administrative staff. This narrative will also describe how active TB is diagnosed and treated, how LTBI prophylaxis and contacts are presently managed, plus the diagnostic capacity of the facility (eg whether Chest X-rays are done on site).

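### The 80% power statement uses 24 equal clinics of at least 100 contacts; the protocol's own figures give other clinic counts and sizes, and with Table 1 sizes the 80% depends on an unstated GEE weighting

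*Protocol*

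**What the plan says.** The Study design section states: "We propose a cluster randomized trial at 36 sites in 6 countries". The Preamble lists six countries, including Brazil. The text before Table 3 refers to five countries besides Canada, and the section on importance and next steps counts Canada plus five others.

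The sample size section states: "We will have 24 clusters in 5 countries". It says that its cluster sizes come from Table 1, which lists 24 randomisation units in five countries, without Brazil. It then takes "at least 100 contacts per site every 6 months (based on minimum 40 active cases every year, and estimated 4.2 contacts per index case", and concludes for a 10% baseline and an ICC of 5%: "we would have 80% power to detect a 10% increase in proportion of contacts starting therapy". Every row of Table 2 uses 100 contacts per clinic.

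Under Selection of sites, each clinic "should have diagnosed an annual average of at least 40 patients with active pulmonary TB in each of the preceding 3 years".

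The data analysis section for Phase 2 specifies individual-level GEE with an identity link and jack-knife variance on contacts from the final 6 months. It says that this handles varying cluster sizes and is robust to a misspecified correlation structure. It names no working correlation.

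**The concern.** In a cluster trial, power depends on how many units are randomised, how large they are, and how their data are weighted. The protocol contradicts itself on the first two. On the third it leaves open a choice to which its power figure is sensitive.

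The robustness that it claims for GEE concerns valid standard errors. It does not preserve power: when a few clinics are very large, an analysis that weights every contact equally lets those clinics dominate and loses effective sample size. A reader who takes the 80% at face value cannot see this, because Table 2 treats all clinics as the same size.

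**Working it through.** **Inputs.** From the sample size section: control proportion 0.10 (0.30 as alternative), difference 0.10, ICC 0.05, alpha 0.05 (two-sided assumed; the protocol does not say), 12 clinics per arm. From Table 1: contacts over 18 months and units per country.

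**1. The plan's own figure.** Design effect = 1 + 99 × 0.05 = 5.95. Effective n per arm = 1200/5.95 = 201.7. Power for two proportions with pooled variance under the null:

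Φ{[d√n − 1.96√(2p̄(1−p̄))] / √(p₁(1−p₁) + p₂(1−p₂))}

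= Φ{[0.10 × 14.20 − 1.96 × 0.505] / 0.500} = Φ(0.86) = 80.5%, detectable difference 0.099. The stated 80% and 0.10 are reproduced.

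**2. Contacts per clinic in 6 months.** The stated basis gives 40/2 × 4.2 = 84. Table 1 gives:

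| Country | Contacts, 18 months | Units | Per unit, 6 months | Cases per unit-year |
|---|---|---|---|---|
| Canada | 1575 | 4 | 131 | 62.5 |
| Benin | 3150 | 2 | 525 | 250 |
| Ghana | 1900 | 2 | 317 | 150 |
| Indonesia | 1900 | 8 | 79 | 37.5 |
| Vietnam | 1900 | 8 | 79 | 37.5 |

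The mean is 145 and the coefficient of variation 0.91. Sixteen of the 24 clinics fall below 84 contacts and, on average, below the 40-case minimum. The four clinics in Benin and Ghana hold 1683 of 3475 contacts (48%).

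**3. Effect of 84 instead of 100.** Effective n = 12 × 84/(1 + 83 × 0.05) = 195.7; power 79.3%, detectable difference 0.101.

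**4. Effect of 36 clinics.** Effective n = 18 × 100/5.95 = 302.5; power about 93%. The 8 Brazilian pilot facilities do not explain the gap, since 24 + 8 = 32.

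**5. Table 1 sizes, ICC 0.05.**
- Independence working correlation (each contact weighted equally): effective n per arm = ½(Σm)²/Σ[m(1 + (m−1)ICC)] = ½ × 3475²/49,351 = 122.
- Exchangeable working correlation: effective n per arm = ½Σ[m/(1 + (m−1)ICC)] = ½(16 × 16.13 + 4 × 17.47 + 2 × 18.87 + 2 × 19.30) = 202.
- Equal clinic weights: effective n per arm = ½K²/Σ[(1 + (m−1)ICC)/m], with K = 24, = 201.

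| Analysis | Effective n per arm | Power, 10% v 20% | Detectable, 10% baseline | Detectable, 30% baseline |
|---|---|---|---|---|
| Table 2 (24 × 100) | 202 | 80.5% | 0.099 | 0.134 |
| Table 1 sizes, exchangeable | 202 | 80.6% | 0.099 | 0.134 |
| Table 1 sizes, independence | 122 | 59% | 0.133 | 0.174 |

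At ICC 0.10 the detectable differences under independence are 0.197 and 0.243, against 0.141 and 0.183 under exchangeable weighting.

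**The case against.** The strongest reply is that Table 2 is right for the Table 1 sizes under a standard GEE specification. Exchangeable weighting gives the same effective n as 24 clinics of 100, and a working correlation is commonly left to the statistical analysis plan. This stands: its absence from the protocol is not itself a fault. What remains is that the protocol's power figure holds under only one of the analyses that its text allows.

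A reader might infer that the trial is underpowered. The documents do not support that. The loss to 59% arises only under independence, which the protocol does not select. Even then, power for a 15-point difference from a 10% baseline at ICC 0.05 is about 87% (68% from 30%). At ICC 0.02, the upper value that the protocol reports from its earlier trial (for treatment completion), independence still gives about 91% for 10 points.

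A reader might also set "We wish to detect a 15% increase in the proportion of contacts that initiate therapy" against the Table 2 row that shows 0.18 and call it an error. It is not: the row is printed openly, and the closing sentences claim only 10 points, or near 13 at a 30% baseline.

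Nor do the documents settle that the trial is 24 clinics without Brazil. Table 1, the interview numbers, the jurisdictions and the solution budgets all cover five countries, and Brazil is described as a pilot. Four other places indicate six. Only reconciliation can be asked for.

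Finally, the 37.5 cases per unit-year come from rounded anticipated country totals, so the shortfall against 40 may be a matter of rounding. The two figures still need to agree.

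**Conclusion.** The contradictions in clinic count, country count and contacts per clinic are real and touch the stated basis of the power claim. Their direct effect is small or favourable: about one power point lost for 84 instead of 100, and a gain to about 93% if there were 36 clinics of 100.

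The substantive point is conditional. With the protocol's own clinic sizes and ICC 0.05, power for 10% versus 20% is about 81% or about 59%, according to the weighting.

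These figures assume equal clinic sizes within each country, an even split of contacts between arms, no precision gain from stratifying by country, and a normal reference distribution. A t reference with 22 degrees of freedom lowers the 24-clinic figures by about 3 points (24 × 100 becomes 77.5%).

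**What to change.** 1. State one number of randomised clinics and countries, and make the Preamble, Study design, Table 1, the sample size section (including the text before Table 3) and the closing section agree. Say whether the Brazilian pilot clinics are in the primary analysis.
2. Replace the figure of 100 contacts with 84 or with the Table 1 sizes. Reconcile the 40-case minimum with the Indonesia and Vietnam counts.
3. Recompute Table 2 with the Table 1 sizes.
4. Specify an exchangeable working correlation, or equal clinic weights, for the primary GEE, so that the stated power holds.
5. Optionally, note beside the 15-point target that its power at 30% baseline and ICC 0.10 is about 63%, as the printed 0.18 already implies.

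The cost is restated figures and one line on weighting, with no added clinics. Near-equal clinic weights give Benin and Ghana less influence than their 48% share of contacts, so if the effect varies with clinic size the estimate is closer to a clinic average than a contact average. The protocol should say that this is intended.

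### The claim of sufficient power for a 27-point effect in Canada rests on a normal approximation with three clinics per arm; power at ICC 0.05 is about 58%, or about 27% with the four clinics planned

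*Protocol*

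**What the plan says.** All figures are in the protocol, under Sample size considerations.

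- **Canada (Table 3).** The heading gives "alpha=.05, and Power = 80" per cent. The bold row has control proportion 0.30, 100 contacts per clinic, ICC 0.05, 300 contacts per arm and detectable difference 0.27. The text concludes: "in Canada, we should have sufficient power to detect a 27% increase in proportion of infected contacts starting LTBI therapy, if 30% now start therapy". It adds that 300 contacts per clinic would lower the detectable difference only to 25%.
- **Whole trial (Table 2).** The inputs are "We will have 24 clusters in 5 countries", "with at least 100 contacts per site every 6 months", and "assuming that at baseline only 10% of contacts are started on Latent TB therapy, plus an ICC of 5" per cent. The matching row reads "0.10 100 6.0 1214 0.05 0.10", and the text states that "we would have 80% power to detect a 10% increase in proportion of contacts starting therapy". The target given at the start of the section is a 15% increase.
- **Number of Canadian clinics.** Table 1 lists 4 randomisation units for Canada, and the section on selecting solutions for Phase 2 gives four cities with one clinic each. Table 3 has 300 per arm at 100 per clinic, and 150 per arm at 50 per clinic. Both imply 3 clinics per arm, or 6 in total.

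The protocol does not name the quantiles behind either table and mentions no small-sample allowance.

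**The concern.** A design effect inflates the variance for clustering. It does not allow for the fact that the between-clinic variance is itself estimated from the clinics. With 24 clinics that omission costs little. With four to six clinics the reference distribution has about 2 to 4 degrees of freedom, and a normal approximation is no longer adequate.

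The within-country analysis is a planned secondary analysis, and the protocol affirms that Canada has enough power for it. Canada is also the setting from which the protocol hopes to generalise to other high-income countries. If the power is far below 80%, readers have a false basis for interpreting a non-significant Canadian result.

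**Working it through.** **Inputs.** Alpha 0.05 (two-sided assumed) and power 80% come from the table headings. Control proportion p1, contacts per clinic m, ICC and stated difference come from the table rows. Clinics per arm k is 12 overall (24/2), 3 for Canada as implied by Table 3 (300/100), or 2 for Canada as planned (4/2).

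**Formulas.** Design effect DE = 1 + (m - 1) x ICC. SE = sqrt{[p1(1-p1) + p2(1-p2)] x DE / (k m)}. Normal power = Phi(difference/SE - 1.96). The t version uses the noncentral t with noncentrality difference/SE and 2k - 2 df.

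**Step 1: reproduce Table 3.** In the bold row p2 = 0.57, DE = 1 + 99 x 0.05 = 5.95, and the variance sum is 0.2100 + 0.2451 = 0.4551.

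- k = 3: SE = sqrt(0.4551 x 5.95/300) = 0.0950; ratio 0.27/0.0950 = 2.84; normal power Phi(0.88) = 81%.
- Over all six rows the same formula gives 80.3% to 82.7%. For the remark on 300 contacts per clinic it gives 79.3%.
- A t calculation on 4 df gives 57% to 59% over the six rows. Table 3 therefore fits normal quantiles with 3 clinics per arm and does not fit a t allowance.

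**Step 2: few-clinic correction, then the clinic count (0.30 versus 0.57, ICC 0.05, m = 100).**

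| Clinics per arm | SE | Ratio | Normal power | t critical value | t power | Detectable, normal | Detectable, t |
|---|---|---|---|---|---|---|---|
| 3 (Table 3) | 0.0950 | 2.84 | 81% | 2.776 (4 df) | 57.5% | 0.27 | 0.35 |
| 2 (planned) | 0.1164 | 2.32 | 64% | 4.303 (2 df) | 26.9% | 0.32 | 0.56 |

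Down the normal power column (81% to 64%) is the effect of the clinic count alone. Across the first row (81% to 57.5%) is the effect of the degrees of freedom alone. With 300 contacts per clinic, the stated 25% becomes 0.33 (3 per arm) or 0.54 (2 per arm).

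**Step 3: the headline in Table 2 (0.10 versus 0.20, ICC 0.05, k = 12).** The variance sum is 0.09 + 0.16 = 0.25; SE = sqrt(0.25 x 5.95/1200) = 0.0352; ratio 2.84. Normal power is 81.1%. With t on 22 df it is 77.5% (77.9% at the printed 1214 per arm). Taking 18 df, to allow for stratification by country, gives 76.6% to 77.1%. The detectable difference on 22 df is 0.104, against 0.0985 with normal quantiles.

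**Step 4: other Table 2 rows at ICC 0.05 and 0.10 (12 clinics per arm, normal to t on 22 df).**

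| Control proportion | ICC | Normal | t, 22 df |
|---|---|---|---|
| 0.10 | 0.10 | 0.139 | 0.147 |
| 0.30 | 0.05 | 0.133 | 0.139 |
| 0.30 | 0.10 | 0.181 | 0.189 |

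With the headline row, the rise is about 0.005 to 0.009.

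**Step 5: the 15-point target (t, 22 df).** Power is 97% (control 0.10, ICC 0.05), 85% (0.30, ICC 0.05) and 81.5% (0.10, ICC 0.10). The remaining case (0.30, ICC 0.10) misses the target, but Table 2 already shows that with its 0.18.

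**The case against.** **The whole-trial part is small.** This stands. The corrected headline difference of 0.104 still prints as 0.10, the loss is 2 to 3 points against the claimed 80%, and uncertainty about the ICC matters more. A reader might infer that the primary comparison is materially underpowered. The protocol's own target of 15 points does not support that.

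**The quantiles are inferred.** This stands in part. The protocol does not name them, and the source cited in Table 3's heading cannot be seen. A reader might say that both tables can be reproduced only with normal quantiles. That goes too far for Table 2, because its two ICC 0.01 rows do not discriminate: one gives about 76% even with normal quantiles, and the other keeps about 80% with t. For Table 3 the six rows agree with each other and exclude a t calculation.

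**The planned analysis is GEE with a jack-knife variance, and its reference distribution may be set elsewhere.** Clinics minus 2 df is an analogue of that analysis, not the analysis itself. This does not rescue the Canadian figure, because a normal-reference Wald test with four to six clusters would not hold its 5% error rate.

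**Canada combines two faults.** This also stands. The 27% should not be put down to the degrees of freedom alone, since part of it comes from Table 3 assuming six clinics where four are planned.

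**The design is not incapable of showing a Canadian effect.** A reader might infer that it is, but the figures do not support this. For 27 points on t, power with 3 clinics per arm is 95% at ICC 0.01 and 85% at ICC 0.02; with 2 per arm it is 57% at ICC 0.01. The weakness depends on the ICC. However, the protocol's conclusion is drawn at 0.05, and the earlier trial's ICC of 0.01-0.02 was for treatment completion, a different outcome.

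**Conclusion.** The statement of sufficient power for Canada is not supported at the ICC it uses. For 27 points from 0.30 at ICC 0.05 and 100 contacts per clinic, power is about 58% on Table 3's own three clinics per arm. With the four clinics planned it is about 27%, and even the normal formula gives only about 64% there. The whole-trial headline is slightly optimistic (about 77-78% rather than 80%), which is a minor matter.

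The result assumes a two-sided 5% test, equal clinic sizes, an even split of clinics between arms, and a between-clinic comparison on clinics minus 2 df. It concerns a secondary analysis and leaves the primary design intact.

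**What to change.** 1. State one number of Canadian clinics and use it throughout, so that Table 3 agrees with Table 1 and the Phase 2 text.
2. Recompute Table 3 with that number and with t quantiles on clinics minus 2 df.
3. Replace the sentence on sufficient power, and the 25% remark for 300 contacts per clinic, with a statement that the Canada-only effect will be estimated, with its confidence interval, without adequate power at ICC 0.05.
4. As a minor correction, restate the headline as about 77-78% power for 10 points (or 80% for about 10.4 points) and update the ICC 0.05 and 0.10 rows of Table 2 on 22 df.

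The cost is recalculation and a few reworded sentences. No clinics, contacts or follow-up need be added.

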Next, the investigators from the country coordinating centres will meet administrators from the participating health facilities - to present the Phase 1 findings, and select the Phase 2 solutions. They will also explain the initial, and in-service training and recording/reporting methods, as well as review general aspect of the diagnosis and treatment of LTBI. The regimen to be used, selected as above by the responsible TB programme, will be reviewed. Note that within each country health facilities fall within one to four municipal or provincial jurisdictions. Therefore in Vietnam (2 provinces with 4 health centres each), and Canada (4 cities with one clinic each) results will be analyzed and presented and interventions selected, using the same options analysis approach described above, at the level of the city or province. On the other hand, all health facilities fall within one city in each of Ghana, Indonesia and Benin – hence Phase 1 results from all health facilities within each country will be used to select country-specific set of solutions. If there are substantial differences in Phase 1 findings between sites within each of these jurisdictions, then some solutions will be site-specific.

*[As examples: In Site A, the indicator data reveals that the step when most contacts are missed is the identification of contacts by newly diagnosed pulmonary TB patients. Responses from the questionnaires and interviews at this same site suggests that this occurs because health workers do not explain, and the patients do not understand the reasons for contact investigation. Therefore one cadre of health workers will be assigned this task (by health officials), and training around a scripted set of messages provided (by research staff) to that cadre of workers. In Site B, indicator data reveals that many contacts with positive TST fail to complete diagnostic evaluation. Questionnaire and interview information suggests this is because contacts must come at least 3 times to complete this – once for TST reading, a second time to see a physician, then a 3rd time to have a chest X-ray done. The intervention suggested will be to organize the service delivery so that all three activities can be completed on the same day – "one stop shopping".]*

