**DATA ANALYSIS FOR PHASE 2****Contact investigation outcomes:**

Among the household contacts, the following outcomes will be measured

1. Contacts identified.
2. **Started LTBI therapy** (primary outcome)
3. Completed LTBI therapy (secondary outcome)

The primary outcome will be the proportion of identified contacts who start LTBI therapy – in the final 6 months of the trial (to account for delayed impact of this complex intervention). If we find that more than 20% of contacts are diagnosed to have active TB, which would be far in excess of published experience, then we would investigate if this reflected over-diagnosis.

Our analysis will be performed at the level of the individual, but will account for correlation between subjects from the same centre. Population averaged logistic regression with an identity link estimated via generalized estimating equations (GEE) and using a jack-knife estimate of the variance will be used to assess the effect of the intervention on the primary and secondary outcomes above, depending on the type of outcome (e.g. count or proportion). This approach will account for the correlation between subjects in the same cluster, and for varying cluster sizes. Using an identity link (rather than a logit link) will allow us to estimate risk differences for binary outcomes.

Population averaged models estimated via GEE are robust to mis-specification of the correlation structure. While our data will surely have clustering at the household level as well, we need only account for the top-level cluster (here centre) and use the empirical standard errors to ensure that our inferences are conservative.

For count type outcomes, we will use a similar approach as described above, but using a Poisson distribution.

In secondary analyses, we will use logistic regression with a logit link estimated via GEE and also adjust for additional confounders (country, age, sex and smear status of index case). In sensitivity analyses we will analyze at the level of the cluster. Missing data will be dealt with via multiple imputation using chained equations which will allow us to impute binary as well as continuous variables .

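### Table 3 of the Protocol claims 80% power for a 27-point difference in Canada on the basis of six clinics; the Protocol gives Canada four, and the denominator changes between calculation and conclusion

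*Protocol*

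**What the plan says.** Under Sample size considerations, the Protocol plans a secondary estimate of the effect within each country and gives a separate table of detectable differences for Canada (Table 3, headed "alpha=.05, and Power = 80" percent). The highlighted row reads "0.30 100 6.0 300 0.05 0.27": control proportion, contacts per clinic, design effect, contacts per arm, ICC and detectable difference. The text concludes that "we should have sufficient power to detect a 27% increase in proportion of infected contacts starting LTBI therapy", "if 30% now start therapy". It adds that 300 contacts per clinic would lower the detectable difference only to 25%. On the ICC it says "to be conservative we will assume this to be 0.05 to 0.1".

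Table 1 lists four randomization units for Canada, with 1575 identified contacts and 450 with LTBI over 18 months. The section on selecting Phase 2 solutions agrees: "Canada (4 cities with one clinic each". A footnote to Table 1 puts LTBI prevalence among contacts at "28.1% in Canada".

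On the denominator, the sample size section bases power on close contacts identified per unit, and the Phase 2 analysis section says: "The primary outcome will be the proportion of identified contacts who start LTBI therapy".

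**The concern.** Every row of Table 3 sets the arm size at three times the contacts per clinic (150 against 50, 300 against 100). That is three clinics per arm, two more in total than Table 1 provides. In a cluster trial the number of clusters largely determines precision, so the table flatters the Canadian comparison.

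The conclusion also refers to infected contacts, although the clinic sizes behind it fit identified contacts. Canada is the only country given its own power statement, and the Protocol expects Canadian findings to carry over to other high-income countries. A reader who trusts the stated power could take a null Canadian result as evidence against an effect when the comparison could not show one.

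**Working it through.** **Inputs.** Control proportion 0.30, target 0.57, ICC 0.05 (also 0.01 and 0.10), 100 contacts per clinic, alpha 0.05 and power 80%, all from Table 3 and its text. Sidedness is not stated; two-sided is assumed.

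**Formulas.** Design effect = 1 + (m − 1) × ICC. Effective size per arm = (clinics per arm × m) / design effect. Power = Φ(difference / SE − 1.96), with SE = √[(p1(1 − p1) + p2(1 − p2)) / effective size]. This is the unpooled-variance form. The Protocol does not state its formula, so ranges below cover the unpooled and pooled-variance forms.

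**Step 1: reproduce the stated 0.27.** Design effect = 1 + 99 × 0.05 = 5.95. Effective size = 300 / 5.95 = 50.4. SE = √[(0.2100 + 0.2451) / 50.4] = 0.095, and 0.27 / 0.095 − 1.96 = 0.88, so power is 81% (79% pooled). The detectable difference is 0.266 (0.274 pooled). The 25% figure for 300 per clinic also comes back: 900 / 15.95 = 56.4, giving 0.252 (0.258 pooled). Both need three clinics per arm. Table 2, by contrast, uses about 1222 / 100 = 12 clinics per arm, which agrees with its 24 clusters.

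**Step 2: use two clinics per arm.** Effective size = 200 / 5.95 = 33.6. SE = 0.116, and 0.27 / 0.116 − 1.96 = 0.36, so power is 64% (61% pooled).

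| Contacts per clinic | ICC | Stated detectable difference | With two clinics per arm |
|---|---|---|---|
| 100 | 0.01 | 0.16 | 0.19 |
| 100 | 0.05 | 0.27 | 0.32–0.34 |
| 100 | 0.10 | 0.36 | 0.42–0.45 |
| 300 | 0.05 | 0.25 | 0.31–0.32 |

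**Step 3: allow for few clusters.** A cluster-level t test on four clinics has 2 degrees of freedom and a critical value of 4.30 in place of 1.96. With noncentrality 0.27 / 0.116 = 2.32, power is about 27%. Six clinics (4 degrees of freedom) would give about 58%.

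**Step 4: try five clinics.** With a 2-versus-3 split at ICC 0.05, power for 27 points is about 69% to 73% by the normal approximation.

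**Step 5: check the denominator.** Per clinic per six months, Table 1 implies 1575 / 3 / 4 = 131 identified contacts and 450 / 3 / 4 = 37.5 infected contacts. The 100 per clinic therefore fits identified contacts.
- Infected contacts: design effect 1 + 36.5 × 0.05 = 2.83, effective size 75 / 2.83 = 26.5, detectable difference 0.36 to 0.38, power for 27 points 51% to 54%.
- Identified contacts (131 per clinic): detectable difference 0.32 to 0.33, power 63% to 66%. Here the 30% baseline already lies above the 28.1% prevalence, which is hard to square with treating only test-positive contacts.

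**The case against.** - **The arithmetic is right.** This stands. The stated differences follow, within rounding and choice of formula, from the table's own inputs. The fault is the number of clinics.
- **The Canadian unit count is itself unsettled.** This also stands. The site descriptions name Montreal, Vancouver, New Westminster, Edmonton and Calgary, which can be read as five, and the design section speaks of 36 sites in 6 countries while the sample size section uses 24 in 5. The two-per-arm figures thus rest on Table 1 and the Phase 2 text. Five clinics also fall short of 80%.
- **The planned analysis is not a t test.** The main method is GEE with a jack-knife variance; cluster-level analysis is a sensitivity analysis. The 27% figure therefore shows how few clusters there are and does not predict the power of the planned model. The case does not depend on it.
- **A 57% target looks impossible when only 28.1% of contacts are infected.** A reader might infer this, but the sentence is about infected contacts, and 57% of those is 0.57 × 0.281 = 16% of identified contacts. What remains is a conflict of denominators.
- **The same ceiling might seem to undermine the 30% rows of Table 2.** The documents do not support this. For Ghana and Vietnam the Protocol describes policies of treating young or HIV-infected contacts without stating a skin-test requirement, so prevalence of positive tests is not an established upper limit on starting therapy.

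**Conclusion.** The claim of sufficient power for 27 points in Canada is not supported by the Protocol's own site numbers. With four units, control 0.30, ICC 0.05, 100 contacts per clinic and a two-sided test, the detectable difference is about five to seven points larger than stated, and normal-approximation power is about 61% to 64% instead of 80%. No reading of the Canadian site list gives the six clinics that Table 3 needs. Separately, the conclusion names a denominator that matches neither the clinic size used nor the primary outcome.

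This should be corrected but is of moderate weight. The within-country estimates are secondary, Table 3 already shows that Canadian precision is poor, and neither the all-country sample size nor the primary analysis depends on it.

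**What to change.** 1. Reconcile the number of Canadian randomization units across Table 1, the site descriptions and the Phase 2 text.
2. Recompute every row of Table 3, and the sentence on 300 contacts per clinic, with that number; preferably use t quantiles suited to so few clusters, and state the formula and sidedness.
3. Use one denominator throughout. If identified contacts, give a baseline compatible with the stated prevalence; if infected contacts, use about 37.5 per clinic per six months.
4. Replace the statement of sufficient power with the recomputed detectable difference, and say that the Canadian estimate will be imprecise.

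The cost is one table and two sentences. No sites, contacts or changes to the primary analysis are needed; the stated Canadian figures become less favourable.
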